8.0 STUDY ASSESSMENTS AND PROCEDURES

- Patients may not complete any Screening Visit Procedures including the Spirometry Assessment unless all prohibited medications/therapy described in Section 6.7.3 have been withheld for the defined time interval.
- Study procedures and their timing are summarized in the SoA.
- Protocol waivers or exemptions are not allowed.
- Immediate safety concerns should be discussed with the Sponsor immediately upon occurrence or awareness to determine if the patient should continue or discontinue blinded study medication.
- Adherence to the study design requirements, including those specified in the SoA, is essential and required for study conduct.
- All Screening evaluations must be completed and reviewed to confirm that potential patients meet all eligibility criteria. The Investigator will maintain a Screening log to record details of all patients screened and to confirm eligibility or record reasons for Screening failure, as applicable.
- Procedures conducted as part of the patient's routine clinical management (eg, blood count) and obtained before signing of the ICF may be utilized for Screening or baseline purposes provided the procedures met the protocol-specified criteria and were performed within the time frame defined in the SoA.
- The maximum amount of blood collected from each patient over the duration of the study, including any extra assessments that may be required, will not exceed 300 mL. Repeat or unscheduled samples may be taken for safety reasons or for technical issues with the samples.
- See Section 5.6 for specific information to be collected for screen failures.

8.1 Screening Assessments and Procedures

8.1.1 Informed Consent

Informed consent must be obtained according to the Informed Consent Process described in Section 11.2.

8.1.2 Demographic Variables

Demographic variables will include items such as age, sex, ethnicity, and race.

8.1.3 Medical/Surgical/ COPD/ and Smoking History

A history of relevant current or past medical conditions, surgical history, COPD history, and smoking history (current or former [yes or no]) will be obtained.

- Minor surgical procedures (eg, tonsillectomy, appendectomy) performed more than 5 years prior to Screening Visit 0 do not need to be recorded.
- COPD history will include COPD exacerbation history and COPD type (emphysema and/or chronic bronchitis), as assessed by the investigator or medical professional). Chronic bronchitis is defined as “regular production of sputum for three or more months in two consecutive years (in the absence of other conditions that may explain it [GOLD, 2020]).”
- Former smokers are defined as those who have stopped smoking for at least 6 months prior to Screening Visit 0.

Medical and COPD condition(s) identified during the Screening Visit will be documented as medical history and not as an AE(s) unless the condition worsens during the study and meets the definition of an AE.

8.1.4 Prior/Concomitant Medications/Therapies

A history of prior medications used will be obtained and recorded as described in Section 6.7.4.

8.1.5 Vital Signs

Vital signs will be completed at Screening per the instructions in Section 8.4.1. In addition, height in centimeters (cm), weight in kilograms (kg), and body mass index will also be measured and recorded at Screening.

8.1.6 Electrocardiogram

12-Lead ECGs will be completed per the instructions in Section 8.4.2.

8.1.7 Chest X-Ray

A CXR (posterior-anterior) will be obtained at Screening or obtained within 12 months prior to Screening. If a CXR within the past 12 months is not available but a CT scan within the same time period is available, the CT scan can be reviewed in place of a CXR.

For subjects in Germany, if a CXR or CT scan is not available in the 12 months prior to Screening, the subject is not eligible for the study, as this assessment will not be conducted at the Screening visit.

8.1.8 Spirometry Assessment

Spirometry at Screening will be completed per the instructions in Section 8.3.1.

8.1.9 Modified Medical Research Council Dyspnea Scale

The mMRC dyspnea scale is a questionnaire that measures COPD symptoms and defines symptom burden at Screening (Fletcher, 1960). Site staff will administer/interview the patient to complete the mMRC dyspnea scale questionnaire.

8.1.10 Clinical Laboratory Assessments

Clinical laboratory tests will be conducted per the instructions in Section 8.4.3. Abnormal chemistry and/or hematology may be repeated during Screening/Run-in.

8.1.10.1 Viral Serology

Viral serology for HBsAg, anti-HBc, anti-HBs, and Hepatitis C Virus will be obtained at Screening. Chronic stable hepatitis B and C is not exclusionary if the patient otherwise meets study entry criteria.

8.1.10.2 COVID-19

Testing for COVID-19 may optionally be completed (Section 11.3) prior to spirometry and following local requirements. Patients with a positive COVID-19 test result indicating an active infection at Screening or anytime between Screening and Randomization will be excluded.

Patients with a positive COVID-19 antibody test from a past exposure who do not exhibit symptoms of an active COVID-19 infection are eligible to participate in the study.

8.1.11 Physical Examination

A complete physical examination will include, at a minimum, assessments of the Cardiovascular, Respiratory, Gastrointestinal, and Neurological systems.

Investigators should pay special attention to clinical signs to ensure patients have had no previous serious illness(es).

8.1.12 Inclusion/Exclusion Criteria

Patient eligibility will be assessed using the inclusion criteria (Section 5.1) and exclusion criteria (Section 5.2).

8.1.13 Electronic Diary Activities

Electronic Diary training will be conducted as described in Section 8.5.4 and the eDiary will be issued for use during the study. Patients will be instructed to enter their daily symptoms (E-RS:COPD/EXACT-PRO questionnaire), rescue medication (puffs per day), and maintenance LAMA or LABA medication (if applicable) into the eDiary each day.

8.1.14 Interactive Response Technology

Patients will be registered in the IRT system (See Section 8.5.2).

8.1.15 Nebulizer Equipment Training

See Section 8.5.5 for details on nebulizer equipment training. At the Screening Visit, site staff will review the information and instructions provided by the manufacturer with the patient (e.g. Instructions for Use, located in the Pharmacy Manual). Hands-on training with the nebulizer equipment will not occur until the Randomization Visit.

8.1.16 Dispense Rescue Medication

Rescue medication (albuterol/salbutamol) will be dispensed for use as needed during the study but must be withheld for at least 4 hours prior to spirometry and should be withheld for at least 4 hours prior to ECGs. See Section 6.7.2 for additional details.

8.2 Randomization Criteria Assessment– Day 1

The criteria for Randomization are described in Section 5.3.

8.3 Efficacy Assessments

Planned timepoints for all efficacy assessments are provided in the SoA (Section 1.3).

8.3.1 Spirometry

Spirometry will be obtained using spirometry equipment provided by the central spirometry vendor that meets or exceeds the ATS minimal performance recommendations [Miller, 2005].

The central spirometry vendor will provide a spirometry manual with additional instructions and details.

All Spirometry will be reviewed and over-read by the central spirometry vendor and the spirometry vendors determination of acceptable endpoint measurements will override determination by the investigative site.

- Acceptable spirometry efforts should have a satisfactory start of test and end of test (plateau in the volume-time curve) and be free from artifacts due to cough, early termination, poor effort, obstructed mouthpiece, equipment malfunction, or other reason [Miller, 2005].
- For FEV₁ and FVC determinations, at least 3 but no more than 8 acceptable spirometry efforts should be obtained.
- The largest FEV₁ and FVC from the 3 acceptable efforts should be recorded, even if they do not come from the same effort.

8.3.1.1 Spirometry Training

Prior to the first spirometry measurement at each clinic visit requiring Spirometry, the site staff will train each patient on how to perform acceptable spirometry maneuvers according to instructions provided by the central spirometry vendor.

8.3.1.2 Spirometry must be performed as follows:

- **Coordination of the timing of spirometry and in-clinic dosing with blinded study medication is critical. See Section 1.4 for the Schedule of Spirometry and In-Clinic Dosing with Blinded Study Medication.**
- Spirometry Start Time: between 06:00 AM and 10:00 AM.
- Health Outcomes: Complete health outcome assessments as described in Section 8.3.3 prior to spirometry.
- Withhold the Following or Reschedule the Visit*:
 - *Blinded Study Medication*: Blinded study medication must be withheld until pre-dose spirometry is completed.
 - *Rescue Medication*: Albuterol/salbutamol must be withheld for ≥ 4 hours.
 - *Maintenance LAMA or LABA medications (or LAMA/ICS or LABA/ICS, if applicable)*: Must withhold Twice-Daily medications for 24 hours and Once-Daily medications for 48 hours prior to spirometry.

****If the withholding periods above are not met, the visit should be rescheduled to be held within 3 days of the scheduled visit.***

- Recommendation/ Request: Patients should refrain from smoking and/or caffeinated beverages prior to Spirometry for the withholding periods below:
 - *Smoking*: No smoking for at least 1-hour prior to each spirometry assessment.
 - *Caffeinated Beverages*: Abstain from drinking beverages with high levels of caffeine (eg, tea, coffee) for 2 hours prior to each spirometry assessment.

8.3.2 COPD Exacerbation Assessment

Guidelines for Identifying COPD Exacerbations for this study are located in Section 11.6.

8.3.3 Health Outcomes

The schedule for all health outcomes assessments are provided in the SoA (Section 1.3).

During Study Visits

All patient reported outcomes administered during study visits should be administered at the beginning of a study visit before any physical activity or spirometry, except for Healthcare Utilization assessment, which can be done at any point during the visit. The following is the recommended order *as applicable for a given visit*:

- mMRC
- SGRQ
- EQ-5D-5L
- Baseline/Transitional Dyspnea Index (BDI)/TDI

8.3.3.1 *St. George's Respiratory Questionnaire*

The SGRQ Patient Reported Outcome (PRO) measure is designed to assess health-related quality of life in patients with COPD in terms of symptoms, daily activity limitation, and psychosocial well-being (Jones , 1991). The SGRQ is completed by the patient.

8.3.3.2 *EuroQol-5-Domain Questionnaire*

The EQ-5D-5L questionnaire is a standardized instrument designed to measure health utility in terms of mobility, self-care, usual activities, pain/discomfort, and anxiety/depression (Szende, 2014). The EQ-5D-5L questionnaire is completed by the patient.

8.3.3.3 *Baseline Dyspnea Index/Transitional Dyspnea Index*

The BDI is used to measure the severity of dyspnea in patients at baseline (Mahler, 1984). Mahler also developed the TDI which measures changes in patient dyspnea from baseline. The instruments are scored based on ratings for functional impairment, magnitude of task, and magnitude of effort. The BDI and TDI are administered by site staff via patient interview.

8.3.3.4 *Healthcare Utilization*

All unscheduled visits to a physician office, visits to urgent care, visits to emergency department, and hospitalizations for any cause and/or related to COPD will be recorded in the eCRF. In addition, visits and contacts that are due to a COPD exacerbation will be assessed at each clinic visit and recorded in the exacerbation form of the eCRF.

8.3.3.5 *Patient Perception Survey*

At the Follow-up contact, the study site will survey each patient regarding patient perception of their study treatment assignment.

At Home

8.3.3.6 *Evaluating-Respiratory Symptoms Questionnaire*

The E-RS is a PRO instrument derived from the EXACT-PRO designed to collect data to quantify the severity of respiratory symptoms across domains of breathlessness, chest symptoms and cough/sputum in patients with COPD and evaluate treatment benefit (Exact 2013). The E-RS is an electronic instrument to be completed by the patient in the form of the EXACT-PRO in the eDiary each evening before bedtime.

8.4 Safety Assessments

Planned timepoints for all safety assessments are provided in the SoA, Section 1.3.

8.4.1 Vital Signs

- Vital signs should be obtained prior to blinded study medication dosing at all visits.
- Temperature in Celsius, pulse rate, blood pressure, and respiratory rate will be assessed. The mode of temperature collection should be noted in the source (e.g. oral, forehead, etc).
- Blood pressure and pulse measurements will be assessed with a completely automated device. Manual techniques will be used only if an automated device is not available.
- Supine blood pressure, respiratory rate, and pulse measurements should be obtained after the patient has been at rest for at least 5 minutes in the supine position and located in a quiet setting without distractions (eg, television, cell phones).

8.4.2 Electrocardiogram

12-lead ECG will be obtained using standardized ECG equipment provided by the centralized vendor. Albuterol/salbutamol should be withheld for at least 4 hours prior to ECG assessments. It is recommended that ECG assessments should be obtained after patients have rested for approximately 5 minutes.

- The central ECG vendor will provide an ECG manual with additional instructions and details.
- All ECGs will be reviewed and over-read by the central ECG vendor and the ECG vendors interpretation of the measurement(s) will override the interpretation by the investigative site, if consensus is not reached.

8.4.2.1 *Randomization/Visit 1: Triplicate ECGs at Pre-Dose*

At Day 1/Randomization/Visit 1 prior to dosing (pre-dose), triplicate ECGs (over a brief period of time) must be performed.

8.4.2.2 *Clinically Significant Abnormality*

Review the ECG Withdrawal Criteria. If a clinically significant ECG abnormality is identified post-randomization, even if the assessment was pre-dose, the ECG Withdrawal Criteria in Section 11.5 should be reviewed and triplicate ECGs (over a brief period of time) should be performed to confirm the abnormality in 2 of 3 measurements.

8.4.2.3 *Recommendation/ Request*

Patients should refrain from smoking and/or caffeinated beverages prior to ECGs for the withholding periods below:

- *Smoking*: No smoking for at least 1-hour prior to each ECG assessment.
- *Caffeinated Beverages*: Abstain from drinking beverages with high levels of caffeine (eg, tea, coffee) for 2 hours prior to each ECG assessment.

8.4.3 Clinical Laboratory Assessments

See Section 11.3 for the list of clinical laboratory tests to be performed and additional instructions.

8.4.3.1 COVID-19

Testing for COVID-19 may optionally be completed (Section 11.3). Patients with a positive COVID-19 test result indicating an active infection anytime during the study will be withdrawn.

8.4.4 Adverse Event Assessment

The method of detecting AE will be performed as described in Section 8.7 and Section 11.7.

8.5 Other Assessments and Procedures

Planned timepoints for all other assessments and procedures are provided in the SoA, Section 1.3.

8.5.1 Concomitant Medication Assessment

Patients must be queried for concomitant medication use at each contact (clinic visit or phone contact). Concomitant medications must be documented in the eCRF. Concomitant medications/therapy and documentation are described in Section 6.7. The list of permitted rescue and background medications is provided in Section 6.7.2. The list of prohibited medications/therapy is provided in Section 6.7.3.

8.5.2 Interactive Response Technology

Sites will enter information into the IRT at specified visits. All patients consented will be assigned a patient identification number upon signing of the ICF.

8.5.3 Randomization

Patients meeting all inclusion criteria (Section 5.1) and all Randomization Criteria (Section 5.3) and meeting none of the exclusion criteria (Section 5.2) will be randomly assigned to blinded study medication via the IRT (Section 8.5.2) at Visit 1.

8.5.4 Electronic Diary Activities

Electronic Diary (eDiary) training will be conducted. Patients will be instructed to enter their daily symptoms (E-RS:COPD/EXACT-PRO questionnaire), administration of their blinded study medication (morning and evening), rescue medication (puffs per day), and maintenance LAMA or LABA medication, or LAMA/ICS or LABA/ICS (if applicable) into the eDiary each day. Electronic Diary compliance will be visually reviewed by the site staff at each clinic visit or discussed with the patient via phone contact and/or when patients are unable to come into the clinic. Patients with poor compliance should be instructed by the site staff to improve eDiary compliance.

8.5.5 Nebulizer Equipment Training

Patients and site staff will be trained on use of the PARI LC Sprint nebulizer and PARI Vios PRO Aerosol Delivery System, and the PARI BOY compressor or equivalent which will be used for inhalation of blinded study medication during the study period. Once the site staff has been trained, they will review the information and instructions provided by the manufacturer with the patient (e.g. Instructions for Use, located in the Pharmacy Manual). Hands on training with the nebulizer will occur at randomization with administration of the first dose of blinded study medication.

8.5.6 Training for Spirometry

Training for spirometry maneuvers will be conducted by the site staff as per the guidelines in the spirometry manual provided by the central spirometry vendor.

8.5.7 Blinded Study Medication Dosing in the Clinic

Blinded study medication dosing in the clinic will be conducted as described in Section 6.1.1.

8.5.8 Dispense/Collect Rescue Albuterol/Salbutamol

Albuterol/salbutamol will be dispensed/collected at specified study visits for use as needed. See Section 6.7.1 for additional detail.

8.5.9 Dispense/Collect Blinded Study Medication

Blinded study medication will be dispensed/collected at clinic visits that include Spirometry.

8.6 Disaster Contingencies

Prospective planning is required for this study due to the increased risk of a regional or global disaster (eg pandemic, natural disaster, terrorism).

8.6.1 Site-Level Disaster Plan

It is recommended that investigative sites prepare a written Disaster Plan for this study which describes how the site will manage patient activities and procedures in the event that site is not operating normally, site equipment is not available, and/or patient(s) cannot attend an in-clinic study visit. This written Disaster Plan could include but not be limited to a description of how the following activities and procedures will be conducted for remote visits or phone/video contact:

- Phlebotomy collection
- Vital signs collection
- Blinded study medication distribution
- Rescue albuterol/salbutamol distribution

8.6.2 Flexible Clinic Visits

The SoA includes one scheduled flexible visit at Week 36. A flexible visit will either be:

- An *in-clinic visit* if the site is operating normally and the patient is not restricted from going to the clinic
- A *remote visit* if the patient is restricted from going into the clinic due to a regional or global disaster or the site must limit operations due to a regional or global disaster.
- A *phone or video contact* if an in-clinic visit or a remote visit cannot be conducted due to a regional or global disaster.

8.6.2.1 In-Clinic Visit

All scheduled procedures as per the SoA should be completed if possible (Section 1.3).

8.6.2.2 Remote Visit

Complete as many of the following scheduled visit procedures per the SoA (Section 1.3) with the available equipment as possible:

- Vital signs
- Electrocardiogram (if only one of pre-dose or post-dose ECG collection is possible, post-dose ECG collection should be prioritized)
- Laboratory Tests
- Blinded Study Medication and/or Rescue Medication: See instructions in Section 8.6.3.1.

8.6.2.3 Phone or Video Contact

In the event that patient(s) cannot come to the clinic for a scheduled study visit or a remote visit is not possible, any clinic visits may be conducted by telephone or video. Procedures scheduled for that visit (eg, laboratory procedures, spirometry, ECG) may be collected at a subsequent visit.

The following assessments should be conducted via telephone or video discussion with the patient:

- Concomitant medications (Section 8.5.1)
- Adverse events (Section 8.4.4)
- COPD exacerbation (Section 8.3.2)
- Healthcare utilization (Section 8.3.3.4)
- eDiary activities (as many as possible; Section 8.5.4)

8.6.3 **Unscheduled Visit**

8.6.3.1 *Blinded Study Medication and/or Rescue Medication*

If blinded study medication and/or rescue albuterol/salbutamol cannot be dispensed at a scheduled clinic visit or if a patient will likely run out before attending a scheduled clinic visit, the medication may be dispense alternatively in line with according to local requirements.

Blinded study medication and/or rescue medication can be collected, and compliance can be assessed at the next in-clinic visit.

8.6.3.2 *Study Supplied Nebulizer Replacement*

If a study supplied nebulizer cannot be distributed at a scheduled clinic visit, the study supplied nebulizer may either be picked-up by the patient directly outside the clinic, sent to the patient's home via trackable mail/postal service (unless restricted by local requirements) or given to the patient at the next scheduled visit.

8.6.3.3 *Other Contingencies*

- eDiary: In the event of a problem with the eDiary, a replacement may either be picked-up by the patient directly outside the clinic or sent to the patients home according to local requirements.
- Rescue medication (albuterol/salbutamol): In the event that albuterol/salbutamol is in short supply/not available in a given country or region, another medication may be substituted following consultation and approval by the Medical Monitor (unless restricted by local requirements).
- COVID-19 Testing for Active Disease: A COVID-19 test may be conducted anytime a patient is suspected/exhibiting signs of active disease. If a COVID-19 test is positive for active disease, see Section 7.1.6 for next steps and Section 8.7.9 for AE and other reporting.
- Information relating to disruption of study participation due to COVID-19 will be captured in the eCRF (eg, reason for implementation of contingency measures, reason for missing data and relationship to COVID-19).

8.7 Adverse Events

The definitions of an AE or SAE can be found in Section 11.7.

Adverse events will be reported by the patient.

The Investigator and any designees are responsible for detecting, documenting, and recording events that meet the definition of an AE or SAE and remain responsible for following up AEs that are serious, considered related to the blinded study medication or study procedures, or that caused the patient to discontinue the study (Section 11.7).

As stated in Section 8.1.3, medical and COPD condition(s) identified during the Screening Visit will be documented as medical history and not as an AE unless the condition worsens during the study and meets the definition of an AE.

8.7.1 Time Period and Frequency for Collecting AE and SAE Information

AEs and SAEs will be collected from time of first dose of blinded study medication through the follow-up contact with one exception. Serious Adverse Events assessed as related to study participation (eg, study treatment, protocol-mandated procedures, invasive tests or change in existing therapy) will be collected from the time of consent through the follow-up contact.

All SAEs will be recorded and reported to the Sponsor or designee within 24 hours, as indicated in Section 11.7. The Investigator will submit any updated SAE data to the Sponsor designee within 24 hours of it being available.

Investigators are not obligated to actively seek AE or SAE after conclusion of the study participation. However, if the Investigator learns of any SAE, including a death, at any time after a patient has been discharged from the study, and he/she considers the event to be reasonably related to the blinded study medication or study participation, the Investigator must promptly notify the Sponsor.

The method of recording, evaluating, and assessing causality of AE and SAE and the procedures for completing and transmitting SAE reports are provided in Section 11.7.

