7.2 Study Participation After Discontinuation of Blinded Study Medication

Patients may permanently discontinue blinded study medication before the end of the study if they choose to or at the investigator's discretion.

Patients who permanently discontinue blinded study medication are not required to withdraw from the study unless they test positive for COVID-19 active disease. Patients who have permanently discontinued blinded study medication but do not test positive for COVID-19 active disease and have not withdrawn consent may continue in the study and complete all remaining protocol specified visits.

The Investigator must document the reason for discontinuation of blinded study medication in the eCRF.

Ideally, patients who have permanently discontinued blinded study medication will continue to attend scheduled clinic visits and complete important efficacy and safety assessments. However, if this is not possible then the investigator will encourage the patient to select one of the three options below to participate in as much of the study as they are willing (or able) to participate:

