7.2.1 Reduced Assessments

The patient continues to follow the SoA (Section 1.3) and completes only the following assessments:

- Spirometry
- SGRQ
- COPD exacerbation
- AE
- Concomitant medication

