7.2.2 Combination of Phone Contact and Reduced Assessments

The site contacts the patient by phone per the SoA (Section 1.3) to complete the following assessments:

- COPD exacerbation
- SAE
- Concomitant medication

In addition, the patient returns to the clinic at Week 24 (and Week 48 if in the Week 48 stratum) to complete the following assessments:

- Spirometry
- SGRQ
- COPD exacerbation
- SAE
- Concomitant medication

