7.2.3 Phone Contact Only

The site contacts the patient by phone per the SoA (Section 1.3) to complete the following assessments:

- COPD exacerbation
- SAE
- Concomitant medication

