17.1. ADVERSE EVENTS

Adverse Events (AEs) will be coded using MedDRA central coding dictionary. The version of MedDRA to be used will be specified prior to database lock.

Treatment-emergent adverse events (TEAEs) are defined as AEs that started or worsened in severity on or after the first dose of study medication. Laboratory or ECG findings from procedures or samples drawn prior to the first does of study medication that are assessed/overread after randomization will be considered pre-treatment.

In the case where it is not possible to define an AE as treatment-emergent or not, the AE will be classified by the worst case; i.e. treatment-emergent.

See Appendix 2 for handling of partial dates for AEs.

An overall summary of number of patients within each of the categories described in the sub-section below, will be provided as specified in the shells. The summary AE tables will be presented for overall (up to the end of study for all patients) and separately for data up to week 24 visit (regardless of which treatment duration stratum a patient is randomized into) and data from week 24 up to week 48 visit.

In addition, the number of patients with each of the following AE events will be presented by SOC and PT and summarized by treatment group and different period (i.e. Treatment period (+3

[REDACTED]	[REDACTED]	[REDACTED]	[REDACTED]
[REDACTED]	[REDACTED]	[REDACTED]	[REDACTED]
[REDACTED]	[REDACTED]	[REDACTED]	[REDACTED]
[REDACTED]	[REDACTED]	[REDACTED]	[REDACTED]

days), Follow-up (last dose + 4 days) and Overall). These will also be presented for overall, up to week 24 visit, and from week 24 up to week 48 visit:

- TEAE
- TEAEs causally related to study medication
- Serious TEAEs
- TEAEs with an outcome of death
- TEAEs leading to discontinuation of blinded study medication
- TEAEs leading to withdrawal from study (TEAEs with a diagnosis of COVID-19, TEAEs with no diagnosis of COVID-19)
- TEAEs by maximum severity (Mild, Moderate, Severe)

AEs will be identified by using the “Adverse Events” page of the eCRF. Listings will include TEAEs and Non-TEAEs.

Treatment period is defined as the period from the date and time of first dose up to the last date and time of last dose.

Follow-up is defined as the period from after the date and time of last dose up to the last date recorded on the study.

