APPENDIX 2. PARTIAL DATE CONVENTIONS

Imputed dates will NOT be presented in the listings.

ALGORITHM FOR TREATMENT EMERGENCE OF ADVERSE EVENTS:

START DATE	STOP DATE	ACTION
Known	Known/Partial/ Missing	If start date < study med start date, then not TEAE If start date >= study med start date, then TEAE
Partial, but known components show that it cannot be on or after study med start date	Known/Partial/ Missing	Not TEAE
Partial, could be on or after study med start date OR Missing	Known	If stop date < study med start date, then not TEAE If stop date >= study med start date, then TEAE
	Partial	Impute stop date as latest possible date (i.e. last day of month if day unknown or 31st December if day and month are unknown), then: If stop date < study med start date, then not TEAE If stop date >= study med start date, then TEAE
	Missing	Assumed TEAE

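### Two of the three fallback options after stopping study drug list only SAEs, so capture of later non-serious AEs, which the SAP still counts as treatment-emergent, depends on the option chosen

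*Protocol*

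**What the plan says.** **Collection rule.** Protocol 8.7.1 states: "AEs and SAEs will be collected from time of first dose of blinded study medication through the follow-up contact with one exception". The exception lets SAEs related to study participation be collected from consent. It does not exempt patients who have stopped study drug.

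**After stopping drug.** Protocol 7.2 makes full attendance the preferred path: "Ideally, patients who have permanently discontinued blinded study medication will continue to attend scheduled clinic visits and complete important efficacy and safety assessments". It continues: "However, if this is not possible then the investigator will encourage the patient to select one of the three options below".

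- 7.2.1 has the patient follow the Schedule of Activities, and the patient "completes only the following assessments". The list includes AE.
- 7.2.2 combines phone contact with clinic visits: "In addition, the patient returns to the clinic at Week 24 (and Week 48 if in the Week 48 stratum) to complete the following assessments". The phone list and the clinic list both say SAE; neither says AE.
- 7.2.3 is phone only: "The site contacts the patient by phone per the SoA (Section 1.3) to complete the following assessments". The list says SAE.

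**Counting rule.** SAP 17.1: "Treatment-emergent adverse events (TEAEs) are defined as AEs that started or worsened in severity on or after the first dose of study medication". The algorithm in SAP Appendix 2 for a known start date is "If start date >= study med start date, then TEAE". Neither sets an upper limit after last dose. SAP 17.1 tabulates AEs by system organ class (SOC) and preferred term (PT) for the treatment period plus 3 days, for follow-up, and overall. Each is shown for the whole study, up to Week 24, and from Week 24 to Week 48. The overall summary table has the whole-study and Week 24 cuts, but no on-drug/off-drug split is stated for it.

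**The concern.** The collection rule and the counting rule cover the whole time on study, but two of the three fallback options do not prompt for everything that is counted. Suppose two patients stop drug on the same day and later have the same non-serious event. Under 7.2.1 the site is told to ask about it; under 7.2.2 or 7.2.3 it is told to ask about SAEs only. Both patients stay in the denominator of the TEAE percentages, and SAP 7.3 does not impute missing safety data.

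Safety over 24 and 48 weeks is a stated objective, and the 48-week subset exists for long-term safety. Stopping drug is also tied to clinical course: Protocol 11.6.7 discontinues study treatment after a second or a severe exacerbation, and exacerbation is itself an efficacy outcome. Stopping rates could therefore differ by arm. If they do, or if the option chosen does, the off-drug part of the AE comparison would partly reflect how events were asked about. Neither document explains the difference between the options or adjusts for it.

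**Working it through.** The plan states no figure for this point, so there is none to reproduce. The check sets the texts side by side; an illustration of scale follows.

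**1. What each path asks about**

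| Path after stopping drug | Section | Item listed |
|---|---|---|
| Full attendance (preferred) | Protocol 7.2 and 1.3 | AE assessment |
| Reduced assessments | Protocol 7.2.1 | AE |
| Phone plus clinic at Week 24/48 | Protocol 7.2.2, both lists | SAE |
| Phone only | Protocol 7.2.3 | SAE |

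Two of the three fallback options are SAE-only.

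**2. When the gap begins.** Protocol 7.1 asks patients who stop drug, other than for COVID-19, to complete the Section 7.3 assessments promptly. The early-termination column of the Schedule of Activities includes an AE assessment. The gap therefore mainly concerns events arising after that visit.

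**3. Which outputs are affected**

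- Follow-up and Overall TEAE tables, including their up-to-Week-24 and Week 24 to 48 versions: affected.
- Overall TEAE summary: affected.
- Treatment period (+3 days) tables by SOC and PT: largely unaffected, because off-drug events are separated out.
- SAE and death counts: largely unaffected, because every option collects SAEs.

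**4. The split itself is not settled.** SAP 17.1 first puts the boundary at last dose plus 3 days, with follow-up from last dose plus 4 days. It then defines the treatment period as ending at last dose and follow-up as starting straight after. An AE starting 2 days after last dose falls in the treatment period under the +3-day boundary and in follow-up under the last-dose boundary.

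**5. Illustration of scale (every rate is assumed).** Share of an arm with at least one TEAE that would be missed:

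m = d × s × q × (1 − p0)

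- d: share stopping drug but staying in the study, 5% to 25%
- s: share of those on an SAE-only option, 0% to 100%
- q: chance of a non-serious AE in the remaining off-drug time, 10% to 50%
- p0: share already counted with a TEAE; 0 gives the maximum, 40% is an alternative

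Planned arm sizes are 500 and 300 (Protocol synopsis).

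| d | s | q | m at p0 = 0 | m at p0 = 40% |
|---|---|---|---|---|
| any | 0% | any | 0 | 0 |
| 10% | 50% | 30% | 0.10 × 0.50 × 0.30 = 1.5 points | 1.5 × 0.6 = 0.9 points |
| 25% | 100% | 30% | 0.25 × 1 × 0.30 = 7.5 points | 4.5 points |
| 25% | 100% | 50% | 0.25 × 1 × 0.50 = 12.5 points | 7.5 points |

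In the middle case at p0 = 0, this is 0.015 × 500 = 7.5 patients on ensifentrine and 0.015 × 300 = 4.5 on placebo. If all four rates are equal in the two arms, m is the same in each and the difference in TEAE percentages does not move. A shift requires at least one rate to differ by arm.

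**The case against.** The strongest reply is that the SAE-only lists are a retention trade-off for patients who cannot attend in full, and that other duties fill most of the gap. Only 7.2.1 calls its list exclusive; 7.2.2 and 7.2.3 do not. Protocol 8.7 keeps the investigator responsible for detecting and recording AEs, with no off-drug exception. Protocol 8.7.3 requires patients with a reported AE to be followed at later contacts. A non-serious event that a patient volunteers should therefore still be recorded, and a reader who infers that sites on these options must stop recording non-serious AEs goes beyond the text. What remains is that the lists do not prompt for such events, so capture can vary.

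The conflict with 8.7.1 also depends on which follow-up contact ends AE collection. Protocol 4.1 provides one 4 to 10 days after the last scheduled visit and one 4 to 10 days after an early-termination visit. If the second applies to a patient who stops drug and stays, the conflict with 8.7.1 narrows. Full attendance and 7.2.1 would still collect later AEs that the other two options do not list, so the dependence on option stands.

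Two stronger readings are not supported:

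- **The tolerability events behind stopping are lost.** The assessments triggered at discontinuation include AEs, and the SAP already separates the treatment period in its SOC and PT tables.
- **Up to a quarter of patients are affected** (25% of 800 = 200). The 25% in Protocol 9.2 is a study-withdrawal threshold, which describes a different group. Patients who stop drug and then attend in full or use 7.2.1 lose nothing.

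Similarly, a patient who stops at Week 6 and chooses phone contact could go 18 of 24 weeks (75%) or 42 of 48 weeks (87.5%) without a listed non-serious AE question. Those are upper limits, because the early-termination visit and the contact after it both include AE assessment.

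**Conclusion.** The inconsistency stands. Protocol 8.7.1 and 7.2.1 call for all AEs, 7.2.2 and 7.2.3 list only SAEs, and the SAP counts TEAEs without an end date. Capture of non-serious AEs arising after the early-termination assessments can therefore depend on the option chosen. The reach is limited to Follow-up and Overall TEAE counts and the overall summary, for patients on the two SAE-only options.

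The effect may be small, and is zero if nobody uses those options. The range of 0 to 12.5 percentage points of an arm rests wholly on assumed rates and is not an estimate for this trial. A reader might infer that the AE comparison is biased for or against ensifentrine; the documents do not support this, because they show no difference between arms in stopping, in option chosen or in off-drug AE rates. The correction is still worthwhile because it is cheap and uncollected non-serious events cannot be reliably recovered later.

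**What to change.** **Protocol.** In both lists of 7.2.2 and in 7.2.3, replace SAE with AE and SAE, to match 8.7.1 and 7.2.1. State which follow-up contact ends AE collection for a patient who stops drug but stays in the study.

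**SAP 17.1.** Apply the existing treatment-period/follow-up split to the overall TEAE summary as well. Reconcile the +3-day and +4-day boundaries with the period definitions given later in the same section.

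**Cost.** The contacts already take place, and Protocol 8.6.2.3 already collects AEs by phone or video when visits are disrupted. The price is slightly longer calls, some extra AE entries, and a protocol amendment with the ethics approval and, where applicable, regulatory approval that Protocol 11.2 requires.
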